The following guidelines should be applied.

- Each subject may be allowed up to 3 study drug dose reductions according to protocol-specified dose modifications for AEs. Prospective sponsor medical monitor approval is required for the third dose reduction ([Table 5](#)). Note: the minimum daily dose allowed in the study is 50 mg.
- Treatment-related toxicity will be managed as detailed in [Table 6](#), and additional guidelines in the protocol, or following institutional guidelines. Management of related toxicity, including during a period of study treatment hold, will continue until the toxicity is stable at Grade ≤ 1 , returns to baseline, or in accordance with the assessment of the treating physician.
- If treatment is resumed at the same dose of study drug, and the same toxicity recurs with the same or worse severity regardless of duration, dose must be reduced to the next lower dose

level. If treatment is resumed at the lower dose of study drug, and the same toxicity recurs with the same or worse severity, the subject should have a second dose reduction.

- Subjects who permanently discontinue the study drug for a study-related AE or an abnormal laboratory value must be followed up as described in Section [7.2.5.2](#).
- Study drug must be permanently discontinued for a delay of >14 days due to a treatment-related toxicity and may only be restarted with written permission of the medical monitor if (1) the delay is not due to an AE that requires permanent study drug discontinuation as provided in [Table 6](#), and (2) the subject has not met other criteria requiring study drug discontinuation as provided in Section [8](#), and (3) it is the investigator's opinion that no safety concerns are present. In situations where a delay of >14 days is needed for a treatment-related AE requiring permanent study drug discontinuation (see [Table 6](#)), with prospective sponsor medical monitor approval, the delay may be extended to a maximum of 28 days before permanent treatment discontinuation is required.
- If study drug is on hold for ≤ 14 days, and the criteria for restarting treatment are met, study treatment can be restarted on any day from D1 to D21 of a cycle. Study drug should not be restarted on D22 to D28 of a cycle; in such cases, treatment restart must wait until D1 of the next cycle.

Table 5: Dose Reduction Scheme

Dose Reduction	Starting Dose Level 0	Dose Level -1	Dose Level -2	Dose Level -3 ^a

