Grade 3: Average QTc \geq 501 msec; >60 msec change from baseline	
Hold dose of study drug. Two additional ECGs separated by at least 5 minutes should be performed to confirm the finding. If the finding is confirmed, monitor subject with hourly ECGs until the QTcF has returned to baseline and perform further monitoring as clinically indicated.
 
• Exclude other causes of QTcF prolongation such as hypokalemia, hypomagnesemia and decreased blood oxygenation.• Subjects should receive appropriate electrolyte replacement and should not receive further study drug until electrolytes are documented to be within normal limits. 
Once the QTcF prolongation has resolved to <481 msec, subjects may be re-treated at 1 lower dose level at the investigator's discretion. If not determined to be clinically significant, the subject may resume at the current dose.
 
Single ECG assessments should be performed for 2 additional cycles at the same frequency as in Cycle 1 or as clinically indicated. If abnormality is detected, 2 additional ECGs separated by at least 5 minutes should be performed to confirm the finding.
 
• If ECG assessments show no QTcF \geq481 msec, ECG monitoring will be performed according to the visit schedule for subsequent cycles.• If ECG assessments are still abnormal (QTcF \geq481 msec and \leq500 msec), then ECG monitoring must continue at the same frequency as in Cycle 1 or as clinically indicated, for all subsequent cycles.

Worst Toxicity CTCAE^a (version 5.0) Grade (Unless Otherwise Specified)	Dose Modifications any Time During a Cycle of Therapy
	
Subjects who experience recurrent QTcF \geq501 msec after 1 dose reduction will be discontinued from study treatment.
Grade 4: Torsade de pointes or polymorphic ventricular tachycardia or signs/symptoms of serious arrhythmia	Discontinue study drug.
INVESTIGATIONS-HEMATOLOGY	
Neutrophil Count Decreased (Neutropenia)	
Grade 3 (ANC <1000 - 500/mm ³ [$<1.0 - 0.5 \times 10^9/L$])	Hold dose of study drug until resolved to CTCAE Grade \leq 1 or baseline, then 
If resolved within \leq7 days, maintain dose level of study drug.If resolved between $>$7 days and 14 days, \downarrow 1 dose level of study drug.If not resolved within \leq14 days, discontinue study drug.

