Grade 4 (ANC <500/mm ³ [$<0.5 \times 10^9/L$])	Hold dose of study drug until resolved to CTCAE Grade \leq 1, then \downarrow 1 dose level of study drug. If not resolved within \leq 14 days, discontinue study drug.
Febrile Neutropenia	
Grade 3 (ANC <1000/mm ³ with a single temperature of $>$ 38.3°C [101.0°F] or a sustained temperature of \geq 38.0°C [100.4°F] for $>$ 1 hour)	Hold dose of study drug until resolved to CTCAE Grade \leq 1, then 
If resolved within \leq14 days, \downarrow 1 dose level of study drug.If not resolved within 14 days, discontinue study drug
Grade 4	Discontinue study drug.
Anemia	
Grade 3 (hemoglobin <8.0 g/dL [$<4.9 \text{ mmol/L}$; $<80 \text{ g/L}$]; transfusion indicated)	Hold dose of study drug until resolved or corrected to CTCAE Grade \leq 1 or baseline, then maintain dose level.
Grade 4	Hold dose of study drug until resolved or corrected to CTCAE Grade \leq 1 or baseline, then \downarrow 1 dose level.
Platelet Count Decreased (Thrombocytopenia)	
Grade 3 (platelet <50,000 - 25,000/mm ³ [$<50 - 25 \times 10^9/L$])	Hold dose of study drug until resolved to CTCAE Grade \leq 1 or baseline, then 
If resolved within \leq7 days, maintain dose level of study drug.If resolved between $>$7 days and 14 days, \downarrow 1 dose level of study drug.If not resolved within \leq14 days, discontinue study drug.

Worst Toxicity CTCAE^a (version 5.0) Grade (Unless Otherwise Specified)	Dose Modifications any Time During a Cycle of Therapy
Grade 4 (platelet <25,000/mm ³ [$<25 \times 10^9/L$])	Hold dose of study drug until resolved to CTCAE Grade ≤ 1 or baseline, then \downarrow 1 dose level. 
• If not resolved within ≤ 14 days, discontinue study drug.
INVESTIGATIONS – RENAL	
Serum Creatinine	
Creatinine clearance <30 mL/min (calculated or measured)	Hold dose of study drug until creatinine clearance is ≥ 45 mL/min regardless of grade.
Serum creatinine increase Grade 2 ($\geq 1.5 - 3.0 \times$ ULN or $1.5 - 3.0 \times$ baseline)	Hold dose of study drug until resolved to Grade ≤ 1 or baseline, then: 
• If resolved within ≤ 7 days, maintain dose level of study drug.• If resolved between >7 days and 14 days, \downarrow 1 dose level of study drug• If not resolved within ≤ 14 days, discontinue study drug.

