8 SUBJECT DISCONTINUATION AND STUDY TERMINATION

8.1 **Subject Discontinuation**

8.1.1 ***Discontinuation of Study Drug***

Discontinuation of study treatment does not represent withdrawal from the trial.

If study treatment is permanently discontinued for reasons other than subject's withdrawal of consent, the subject will remain in the study to be evaluated for all study prespecified assessments (such as safety follow-up, efficacy, etc.) See Section [2](#) for data to be collected at the time of discontinuation of study treatment and follow-up.

Subjects must be discontinued from study drug for:

- Local/regional or contralateral invasive or metastatic recurrence (whichever occurs first) by BICR:
 - Subjects should remain on study treatment until local/regional or contralateral invasive or metastatic recurrence is confirmed by BICR.
 - All subjects' imaging (CT/magnetic resonance imaging [MRI] scans) will be read locally and submitted for BICR read, together with any supporting report (including pathology and cytology reports) if a biopsy was conducted (for example, if recurrence was suspected). A central read should be requested at the time of investigator-assessed disease recurrence for confirmation by BICR.
 - If BICR confirms recurrence (local/regional or contralateral invasive or metastatic recurrence, whichever occurs first), the subject must be permanently discontinued from study treatment.
 - If locally diagnosed local/regional or contralateral invasive or metastatic recurrence is not confirmed by BICR, treatment continuation is allowed at Investigator's decision.
 - BICR diagnosis of a local/regional or contralateral invasive or metastatic recurrence, independently from and undiagnosed by local team, will not be communicated to the clinical site.
- Pregnancy.
- 52-week treatment phase completed.
- AE that leads to substantial changes in individual risk-benefit considerations.
- Delay of study drug administration of >14 days (exclusive of scheduled dose interruption, with exceptions noted in Section 7.2.5.1).
- Death.

In addition, subjects may be discontinued from study drug for any of the following reasons:

- New medical condition that does not allow continuation of study drug compliance.
- Protocol deviation, including non-compliance with dosing regimen and retroactive failure to fulfill study entry criteria.

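### Section 7.2.5.1 both bars restart and permits a delay of up to 28 days for the same class of toxicity, leaving 14 time-limited rows of Table 6 without a single stopping rule

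*Protocol*

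**What the plan says.** One bullet in Protocol Section 7.2.5.1 (Dose Modifications and Delays) holds both sentences.

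- **Restart sentence.** The default is "Study drug must be permanently discontinued for a delay of >14 days due to a treatment-related toxicity". Restart needs the medical monitor's written permission and three conditions. The first is that "the delay is not due to an AE that requires permanent study drug discontinuation as provided in" Table 6. The other two are that no other discontinuation criterion in Section 8 has been met and that the investigator sees no safety concern.
- **Extension sentence.** It opens "In situations where a delay of >14 days is needed for a treatment-related AE requiring permanent study drug discontinuation", again pointing to Table 6. It then says that, with prospective approval from the sponsor's medical monitor, "the delay may be extended to a maximum of 28 days before permanent treatment discontinuation is required".

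Table 6 sets the action for each toxicity. Some rows stop drug at once. Others hold it and stop it if recovery takes too long; the Grade 3 febrile neutropenia row, for example, reads "If not resolved within 14 days, discontinue study drug".

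Section 8.1.1 lists among the mandatory reasons for stopping study drug: "Delay of study drug administration of >14 days (exclusive of scheduled dose interruption, with exceptions noted in Section 7.2.5.1".

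**The concern.** Both sentences define their class of events in nearly the same words and by the same table. For that class, the restart sentence makes permission to resume unavailable once the delay passes 14 days. The extension sentence lets the delay continue to day 28 before stopping becomes compulsory. Medical monitor approval does not settle the matter, because whether approval is available is what the two sentences disagree on.

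This is a toxicity stopping rule in a blinded trial, so subject safety comes first. It also decides whether a subject who resumes drug on, say, day 20 has been managed within the protocol or is a deviation. And it bears on whether holds and discontinuations are handled alike from one case to the next.

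**Working it through.** No sample size, power or alpha figure is involved, and the plan states no figure to reproduce. The check sets the texts side by side.

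**Step 1. What each sentence does for the class it names.**

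| | Restart sentence | Extension sentence |
|---|---|---|
| Events | AEs for which Table 6 requires permanent discontinuation | Treatment-related AEs requiring permanent discontinuation, see Table 6 |
| Trigger | Delay over 14 days | Delay over 14 days needed |
| Medical monitor | Written permission, but not open to this class | Prospective approval, open to this class |
| Result on days 15 to 28 | No restart | Delay continues; discontinuation not yet required |

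The disputed interval is 28 − 14 = 14 days.

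**Step 2. Which Table 6 rows could be meant.** Fourteen rows hold drug and discontinue it if the event has not resolved within 14 days:

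1. Neutropenia Grade 3
2. Neutropenia Grade 4
3. Febrile neutropenia Grade 3
4. Thrombocytopenia Grade 3
5. Thrombocytopenia Grade 4
6. Serum creatinine Grade 2
7. Amylase/lipase Grade 3
8. Hypophosphatemia, below 2.0 to 1.0 mg/dL
9. Hypercalcemia Grade 2
10. Pancreatitis Grade 2
11. Vomiting Grade 2
12. Central serous retinopathy and similar events, Grade 2 or 3
13. Other ocular toxicity, Grade 3 or higher
14. Other clinically significant AEs, Grade 3

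None mentions an extension or refers back to the 28-day sentence.

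Two more rows discontinue at 7 days: AST or ALT Grade 3, and combined AST/ALT with bilirubin. Under these rows drug has already been stopped before a delay of over 14 days can arise. The extension reaches them only if it overrides the row, which would move the limit by 28 − 7 = 21 days. The text does not say whether it does.

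Other rows stop drug at once, for example the Grade 4 QTcF row ("Torsade de pointes or polymorphic ventricular tachycardia or signs/symptoms of serious arrhythmia").

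**Step 3. Try to give the class one meaning in both sentences.**

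- Suppose it means only the rows that stop at once. The bar on restart makes sense, but the extension is then empty, because those rows have no hold to lengthen.
- Suppose it includes the 14-day rows. The extension now has something to act on. But once such an event passes day 14, its own row says to discontinue, so it falls under the bar and the permission together.

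No single meaning makes both sentences work unless one sentence is taken to override the other, and the text does not say so.

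**Step 4. Ask whether the extension could be harmless.** It could be read as lengthening the delay without allowing restart. But an extended delay that must end in discontinuation is the same as discontinuation at day 14. The phrase about discontinuation being required only after 28 days has a purpose only if drug can be resumed before then.

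**The case against.** The best defence is that this is a general rule followed at once by a narrower exception. The restart sentence governs a delay that has already overrun. The extension sentence governs approval sought beforehand, with a hard cap, and moves the point at which discontinuation is triggered. A variant assigns the bar to rows that stop at once and the extension to rows with a 14-day limit. Either may be what the authors meant. But the reader has to supply it: the bullet does not mark the second sentence as an exception, both sentences use the same descriptor, and the Table 6 rows carry no such allowance.

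Three stronger inferences are tempting, and the documents support none of them.

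- **That rows which stop drug at once are also in conflict.** They are not. The extension applies only where a delay is needed, and these rows contain no hold.
- **That Section 8.1.1 is a further conflicting rule.** It is not. It defers expressly to Section 7.2.5.1 and takes whatever meaning that section is given.
- **That the discontinuation and hold tables will necessarily differ from case to case.** This is not shown. Both routes past 14 days go through the medical monitor, which limits divergence between sites. The summaries in SAP Sections 8.10.1 and 8.10.3 describe the holds, reductions and discontinuations that occurred, and are not derived from a 14-day or 28-day threshold.

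**Conclusion.** The point holds in a limited form. As written, Section 7.2.5.1 gives incompatible answers on days 15 to 28 for the 14 Table 6 rows with a 14-day limit, and leaves the two 7-day hepatic rows unclear. The conclusion rests on two readings: that a time-limited row counts as requiring permanent discontinuation once its limit has passed, and that extending a delay implies that restart remains possible.

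What is affected is subject safety, the classification of protocol deviations (SAP Section 8.7), and the consistency of holds and discontinuations. The primary DFS analysis is by randomized arm with follow-up continuing after study drug stops, so it is unaffected, as are the sample size and alpha. The SAP also records that the trial closed early for business reasons and will be reported without hypothesis tests. This is a drafting contradiction in a safety rule that should be corrected; it does not threaten the trial's inference.

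**What to change.** Reconcile the two sentences in Section 7.2.5.1 with each other and with the time-limited rows of Table 6. The resulting single rule should state:

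- which events, if any, may exceed the limit in their row with prospective approval, with the 7-day hepatic rows dealt with explicitly;
- whether restart is allowed after an approved extension.

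The affected rows of Table 6 should then carry the rule or a reference to it. Section 8.1.1 needs no change, since its existing cross-reference will follow. Which limit applies is for the sponsor's clinical team, and no view is taken here.

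The cost is protocol wording only, with no new data and no change to the analysis. Because the trial has closed, the practical use now is to settle how delays beyond 14 days are classed when deviations and discontinuations are reported, and to correct the text before it is reused.

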7.2.4 Study Drug Accountability, Handling, and Disposal

Study drug capsules will be received by designated personnel at the study center, handled and stored safely and properly, and kept in a secured location to which only the investigator and

designated study center personnel have access. Upon receipt, study drug should be stored according to the instructions specified on the drug label and in the Investigator's Brochure. Refer to the Pharmacy Manual for further details.

The investigator or designee must maintain an accurate record of the shipment and dispensing of study drug in a drug accountability log. Subjects will be asked to return all used and unused bottles of study drug and packaging on a regular basis, at the end of the study, or at the time of study drug discontinuation. Drug accountability will be assessed by the investigator and/or study personnel, and captured in a subject drug accountability log. This information must be captured in the source document at each subject visit. Drug accountability will be completed by the field monitor during study center visits and at the completion of the study.

At study close-out, and, as appropriate during the course of the study, the investigator will provide access to all used and unused bottles of study drug, packaging, drug labels, and a copy of the completed drug accountability log to the field monitor.

At study close-out, study drug can be destroyed at the study center if permitted by local regulations. Alternatively, the study drug can be destroyed at a third-party depot.

7.2.5 *Dose Modifications for Study Drug*

Subject management and treatment decisions will be based upon Investigator evaluations.

7.2.5.1 *Dose Modifications and Delays*

For subjects who do not tolerate the protocol-specified dosing schedule, dose adjustments are permitted in order to allow the subject to continue the study treatment. For these subjects, the dosing guidelines outlined below will be followed. All dose modifications related to tolerability should be based on the worst preceding toxicity as described in [Table 6](#) (AEs considered possibly related to study drug) and [Table 7](#) (skin toxicity). In addition, per investigator's medical judgment, dose modification (hold) can be applied for subject's safety (eg, perioperatively); the medical monitor must be consulted for dose modifications that are not related to tolerability issues. Dosage changes must be recorded on the Dose Administration page of the eCRF.

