Serum creatinine increase Grade ≥ 2	If serum creatinine CTCAE Grade ≥ 2 has been demonstrated in conjunction with hyperphosphatemia, serum creatinine levels must be repeated at least weekly until resolution. 24-hour urine collection should be obtained as clinically indicated for total phosphate, calcium, protein, and creatinine clearance. Ultrasound examination of the kidneys should be performed as indicated to evaluate de-novo calcifications until resolution or stabilization of creatinine.
Serum creatinine increase Grade ≥ 3 ($>3.0 \times$ ULN or $>3.0 \times$ baseline)	Discontinue study drug.
INVESTIGATIONS – HEPATIC	
Blood Bilirubin Increased (for subjects with Gilbert Syndrome, these dose modifications apply to changes in direct bilirubin only)	
Grade 2 (bilirubin $> 1.5 - 3.0 \times$ ULN if baseline was normal; $>1.5 - 3.0 \times$ baseline if baseline was abnormal)	Hold dose of study drug until resolved to CTCAE Grade ≤ 1 , then: 
• If resolved within ≤ 7 days, maintain dose level of study drug.• If not resolved within ≤ 7 days, \downarrow 1 dose level of study drug.
Grade ≥ 3 (bilirubin $>3.0 \times$ ULN if baseline was normal; $>3.0 \times$ baseline if baseline was abnormal)	Discontinue study drug. Note: If CTCAE Grade 3 or 4 hyperbilirubinemia is due to hemolysis, then \downarrow 1 dose level of study drug and continue treatment at the discretion of the investigator.
AST or ALT Increased	
Grade 3 ($>5.0 - 20.0 \times$ ULN if baseline was normal; $>5.0 - 20.0 \times$ baseline if baseline was abnormal)	Hold dose of study drug until resolved to CTCAE Grade ≤ 1 or baseline, then: 
• If resolved within ≤ 7 days, \downarrow 1 dose level of study drug.• If not resolved within ≤ 7 days, discontinue study drug.
Grade 4 ($>20.0 \times$ ULN if baseline was normal; $>20.0 \times$ baseline if baseline was abnormal)	Discontinue study drug.

Worst Toxicity CTCAE ^a (version 5.0) Grade (Unless Otherwise Specified)	Dose Modifications any Time During a Cycle of Therapy
AST or ALT and Bilirubin Increased	
AST or ALT >3.0 - 5.0 × ULN and total bilirubin >2.0 × ULN without liver metastasis or evidence of disease progression in the liver	Hold dose of study drug until both transaminases and bilirubin resolved to CTCAE Grade ≤ 1 or baseline, then: 
• If resolved within ≤ 7 days, \downarrow 1 dose level of study drug.• If not resolved within ≤ 7 days, discontinue study drug.

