AST or ALT >5.0 × ULN and total bilirubin >2.0 × ULN	Discontinue study drug
LABORATORY/METABOLIC DISORDERS	
Amylase and/or Lipase Increase	
General Comment:	A CT scan or other imaging study to assess the pancreas, liver, and gallbladder should be performed as clinically indicated within 1 week of the first occurrence of any CTCAE Grade ≥ 3 amylase and/or lipase.
Grade 3 (amylase or lipase >2.0 - 5.0 × ULN with signs or symptoms; >5.0 × ULN and asymptomatic)	Hold dose of study drug until resolved to CTCAE Grade ≤ 2 , then: 
• \downarrow 1 dose level of study drug.• If not resolved within ≤ 14 days, discontinue study drug. For recurrent Grade 3 asymptomatic lipase or amylase elevation despite dose reduction, study drug should be held and continuation of therapy should be discussed with the medical monitor following resolution to Grade ≤ 2 .
Grade 4 (amylase or lipase >5.0 × ULN and with signs or symptoms)	For any Grade 4 lipase or amylase elevation, study drug should be held and continuation of therapy should be discussed with the medical monitor following resolution to Grade ≤ 2 .
Hypophosphatemia	
Serum phosphate <LLN - 2.0 mg/dL (0.6 mmol/L)	Maintain dose level of study drug; decrease or hold dose of phosphate binder and optimize standard diet or medical therapy as clinically indicated to increase phosphate level.
Serum phosphate <2.0 - 1.0 mg/dL (<0.6 - 0.3 mmol/L)	Hold dose of study drug until resolved to >2.0 mg/dL (>0.6 mmol/L), then: 
• \downarrow 1 dose level of study drug.• If not resolved within ≤ 14 days, discontinue study drug.
Serum phosphate <1.0 mg/dL (<0.3 mmol/L) (life threatening consequences)	Discontinue study drug.
Hyperphosphatemia	
General Comment:	Optimize dose and schedule of phosphate lowering therapy in accordance with the package insert, or local or institutional guidelines.
Serum phosphate >5.5 - \leq 7.5 mg/dL	Maintain dose level of study drug and optimize phosphate-lowering therapy as clinically indicated.

Worst Toxicity CTCAE ^a (version 5.0) Grade (Unless Otherwise Specified)	Dose Modifications any Time During a Cycle of Therapy

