Grade ≥ 3	Hold dose of study drug until resolution to Grade ≤ 1 . 
 If resolution within ≤ 14 days, \downarrow 1 dose level. If not resolved within ≤ 14 days, discontinue study drug.
OTHER CLINICALLY SIGNIFICANT AEs	
Grade 3	Hold dose of study drug until resolved to CTCAE Grade ≤ 1 , then \downarrow 1 dose level of study drug. 
 If not resolved within ≤ 14 days, discontinue study drug.
Grade 4	Discontinue study drug.

Abbreviations: ADL=activities of daily living; AE=adverse Event; ALT=alanine aminotransferase; ANC=absolute neutrophil count; AST=aspartate aminotransferase; CT= computed tomography; CTCAE=Common Terminology Criteria for Adverse Events; ECG=electrocardiogram; IV=intravenous;

LLN=lower limit of normal; QT=measure of time between the start of the Q wave and the end of the T wave (QT interval) in the heart's electrical cycle; QTc=QT interval corrected for heart rate; QTcF=QTc corrected by Fridericia's formula; ULN=upper limit of normal.

^a CTCAE (v5.0) general guidelines:

Grade 1: Mild; asymptomatic or mild symptoms; clinical or diagnostic observations only; intervention not indicated.

Grade 2: Moderate; minimal, local or noninvasive intervention indicated; limiting age-appropriate instrumental ADL.

Grade 3: Severe or medically significant but not immediately life-threatening; hospitalization or prolongation of hospitalization indicated; disabling; limiting self-care ADL.

Grade 4: Life-threatening consequences; urgent intervention indicated.

Grade 5: Death related to AE.

NOTE: All dose modifications should be based on the worst preceding toxicity. Subjects may have a third dose reduction only with prospective approval of the sponsor medical monitor.

7.2.5.2 *Follow-up for Toxicities*

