10.5.1.5 Adverse Events of Special Interest

The following AEs, if otherwise not qualified as an SAE, are to be reported within 24 hours in the EDC system.

- Potential drug induced liver injury that meets the following criteria (elevation of bilirubin and ALT/AST that meet Hy's Law criteria [[FDA Guidance for Industry 2009](#)]):
 - Treatment-emergent ALT or AST $>3 \times$ baseline value in combination with total bilirubin $\geq 2 \times$ ULN (of which $\geq 35\%$ is direct bilirubin)
 - Treatment-emergent ALT or AST $>3 \times$ baseline value in combination with clinical jaundice.
- Retinal detachment of Grade 3 or higher, regardless of relationship to study drug.
- Keratitis Grade 3 or higher with suspected relationship to study drug.
- Pathological fractures, defined as fractures potentially related or related to metastatic tumor to bone and/or study drug.
- Vascular calcifications with accompanying ischemic AEs.
- Overdose, defined as a daily dose ≥ 200 mg of study drug, and that is associated with an AE that is potentially related to study drug.

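### Table 6: the combined hepatic row for AST/ALT >3.0-5.0 x ULN has no upper bilirubin limit, so its text permits restart where the Grade 3 or higher bilirubin row requires discontinuation

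*Protocol*

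**What the plan says.** All the relevant rules are in Protocol Section 7.2.5.1 and its Table 6, which covers adverse events considered possibly related to study drug.

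- **Bilirubin alone, Grade 3 or higher.** The threshold is more than 3.0 x ULN with a normal baseline, or more than 3.0 x baseline with an abnormal one. The action is to discontinue. One exception is written: "If CTCAE Grade 3 or 4 hyperbilirubinemia is due to hemolysis, then" the dose drops one level and treatment may continue at the investigator's discretion. The bilirubin section carries a limit in its header: "for subjects with Gilbert Syndrome, these dose modifications apply to changes in direct bilirubin only".
- **Combined row, lower transaminase band.** Entry is "AST or ALT >3.0 - 5.0 × ULN and total bilirubin >2.0 × ULN without liver metastasis", and no evidence of progression in the liver. The action is to hold until both analytes are back to Grade 1 or lower, or to baseline. If that takes 7 days or less, restart one level lower; if longer, discontinue.
- **Combined row, higher transaminase band.** "AST or ALT >5.0 × ULN and total bilirubin >2.0 × ULN" leads to discontinuation.
- **General rule.** The section text says "All dose modifications related to tolerability should be based on the worst preceding toxicity as described in" Tables 6 and 7, and the closing note to Table 6 repeats: "All dose modifications should be based on the worst preceding toxicity". Neither sentence says how a combined row ranks against a single-analyte row.

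**The concern.** Take a subject with no liver metastasis or hepatic progression, ALT at 4 x ULN, and bilirubin at 3.5 x ULN from a normal baseline without hemolysis. The bilirubin row says stop for good. The combined row says hold, and allows a restart at a lower dose after quick recovery.

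The direction is the wrong way round. With the same bilirubin and ALT at 2 x ULN, only the bilirubin row applies and the drug is discontinued. Raising ALT to 4 x ULN brings in a row that permits restart. Raising it to 6 x ULN brings in a row that again requires discontinuation.

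What is at stake is re-exposure after a possible drug-induced liver injury. The combined row does not ask for a discussion with the medical monitor before restart, as the Grade 4 amylase/lipase row does.

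**Working it through.** No figure in the plan needs reproducing. The check is to list every combination that reaches a combined row and compare the instructions.

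**Step 1. Six combinations.** Assumptions: normal baselines, no hemolysis, no liver metastasis or progression. Actions are given as *recovered within 7 days / not recovered within 7 days*. Table 6 has no single-analyte transaminase row below Grade 3, which starts above 5 x ULN.

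| ALT/AST (x ULN) | Bilirubin (x ULN) | Strictest single-analyte row | Combined row | Combined row is |
|---|---|---|---|---|
| >3-5 | >2-3 | Grade 2 bilirubin: same dose / reduce | reduce / discontinue | stricter |
| >3-5 | >3 | Grade ≥3 bilirubin: discontinue / discontinue | reduce / discontinue | **looser** |
| >5-20 | >2-3 | Grade 3 ALT/AST: reduce / discontinue | discontinue | stricter |
| >5-20 | >3 | Grade ≥3 bilirubin: discontinue | discontinue | equal |
| >20 | >2-3 | Grade 4 ALT/AST: discontinue | discontinue | equal |
| >20 | >3 | both analytes: discontinue | discontinue | equal |

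The combined row is looser in one of six combinations, and there only for subjects who recover within 7 days.

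**Step 2. Where the overlap starts.** The Grade 3 threshold is 3.0 x ULN with a normal baseline and 3 x baseline with an abnormal one. Exclusion criterion 13a (Section 6.2) caps baseline total bilirubin at 1.5 x ULN outside Gilbert syndrome.

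- Baseline 1.2 x ULN: 3 x 1.2 = 3.6 x ULN.
- Baseline 1.5 x ULN: 3 x 1.5 = 4.5 x ULN.

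The overlap therefore starts between 3.0 and 4.5 x ULN. Every such value exceeds 2.0 x ULN, so outside Gilbert syndrome a Grade 3 or higher bilirubin always meets the bilirubin limb of the combined row. At baseline 1.2 x ULN, a value of 3.5 x ULN is below 3.6 and there is no conflict; at baseline 1.5 x ULN, a value of 5.0 x ULN is above 4.5 and there is.

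**Step 3. Gilbert syndrome.** The bilirubin row uses direct bilirubin, while the combined row uses total bilirubin. The conflict arises only if direct bilirubin is Grade 3 or higher **and** total bilirubin exceeds 2.0 x ULN. The first does not imply the second.

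**Step 4. Does the liver-injury event of special interest close the gap?** Section 10.5.1.5 needs ALT or AST above three times the "baseline value in combination with total bilirubin" of at least 2 x ULN with a direct fraction of at least 35%, or with clinical jaundice. It is a reporting rule and gives no dosing action. Exclusion criterion 13b allows a baseline ALT/AST up to 2.5 x ULN. Since 5.0 / 3 = 1.67, no value in the 3-5 x ULN band can exceed three times a baseline of 1.67 x ULN or more (at baseline 2.5, the threshold is 7.5 x ULN). So some subjects in the overlap meet this event and some do not.

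**The case against.** The strongest reply is that the protocol already gives the answer. The Grade 3 or higher bilirubin row is an unconditional stop with one written exception, hemolysis; a transaminase rise is not an exception. The combined row does not say that it replaces other rows. Where Table 6 wants a row to apply whatever the grade, as for low creatinine clearance, it says so. The worst-toxicity rule is stated twice and points to discontinuation.

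This largely stands. A reader might infer that the protocol directs re-challenge, or leaves the choice wholly open; the documents support neither. Nor does it follow that the worst-toxicity rule fails because the combined rows carry no CTCAE grade. The column header allows categories other than grades, so the worst toxicity need not mean the highest single-analyte grade. What remains is narrower: the combined row describes this subject exactly, and its instruction, read as written, allows restart.

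A second reply is that other safeguards limit the risk. Both rows stop dosing at once. Restart needs recovery of both analytes within 7 days and a lower dose. Section 7.2.5.2 requires at least weekly follow-up for 4 weeks after an interruption. Section 8.1.1 requires discontinuation when an adverse event substantially changes the individual risk-benefit balance, and the DMC reviews safety periodically. These bound the harm, but none of them removes the restart permission from the row.

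**Conclusion.** The inconsistency is real and minor. Within the combined rows it is confined to AST/ALT >3.0-5.0 x ULN with non-hemolytic Grade 3 or higher bilirubin, and the instructions diverge only for subjects who recover within 7 days. Because the combined rows are at least as strict as the single-analyte rows in the other five combinations, the likeliest explanation is a missing upper bound on bilirubin. The six-combination comparison assumes normal baselines; the threshold check extends the overlap to abnormal bilirubin baselines.

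The case is expected to be rare, but the documents do not support a number. A reader might infer an upper bound from the absence of bilirubin among the Grade 3/4 events seen in at least 4% of phase 1 subjects (Protocol Section 3.4.2). That list counts reported adverse events. The same section gives Grade 3 hematology abnormalities separately, so a laboratory grade not reported as an event need not appear in the list.

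No efficacy result changes. The SAP Introduction states that the study was closed early for business reasons, so the point now matters for reading past dosing decisions and for any protocol that reuses this table.

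**What to change.** Add one clause to the combined row for AST/ALT >3.0-5.0 x ULN: *unless the Grade ≥3 bilirubin row requires discontinuation, in which case discontinue study drug.* Hemolysis cases are left as they are, because the bilirubin row does not require discontinuation for them, and the direct-bilirubin limit for Gilbert syndrome is unchanged.

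A general line that the stricter action governs subject to the hemolysis note is tempting but less safe. With hemolytic Grade 3 or higher bilirubin and ALT at 6 x ULN, it could let the note's option to reduce and continue displace the higher combined row's discontinuation.

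The cost is one clause, by clarification letter or amendment, with no change to data collection or analysis. The downside is that a few subjects who recover quickly would lose the option to restart.
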